#### **2.3.3. Patient Exclusion Criteria for Long-term Lenalidomide Maintenance Therapy**

Patients who meet any of the following criteria will be ineligible to receive long-term lenalidomide maintenance therapy as part of this study\*:

1. Patients who have evidence of disease progression prior to enrollment (see Section 3.1 for disease progression definition).

---

\* All patients will be followed for long-term outcomes.

2. Patients who were discontinued from BMT CTN 0702 lenalidomide maintenance therapy, for any reason, prior to the completion of the 3 years of 0702 maintenance.
3. Female patients who are pregnant (positive -BetaHCG) or breastfeeding.
4. Females of childbearing potential (FCBP) or men who have sexual contact with FCBP unwilling to use contraceptive techniques (Appendix B) during the length of lenalidomide maintenance therapy.
5. Patients who experienced thromboembolic events while on full anticoagulation during prior therapy with lenalidomide.
6. Patients unwilling to take DVT prophylaxis.
7. Patients who developed a second primary malignancy, excluding non-melanoma skin cancers after initiation of lenalidomide maintenance therapy on BMT CTN 0702.

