## 2.4. Study Treatments

### 2.4.1. Lenalidomide

Lenalidomide will be administered initially at the patient's last documented dose prior to discontinuation of BMT CTN 0702 lenalidomide maintenance therapy. Cycle duration is 28 days. Patients will continue lenalidomide until disease progression, or discontinuation due to toxicity, death, or withdrawal from the study. Patients who discontinue lenalidomide due to any reason other than death, or withdrawal of consent will continue to be followed per Section 4.4.1

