4.2 Analysis of the Secondary Endpoints

Overall Survival

The event is death from any cause. Overall survival (OS) time will be calculated as the time from randomization on the BMT CTN 0702 protocol to death, loss to follow-up or the end of the study, whichever comes first. CIBMTR data will be used to supplement BMT CTN 0702/07LT data. Patients alive at the time of last observation or lost to follow-up will be censored at the date of last contact either for CIBMTR-reported data or 0702/07LT-reported data. The Kaplan-Meier estimate of survival will be estimated at 5 years post randomization on the BMT CTN 0702 protocol along with corresponding 98.3% confidence intervals. Overall survival will be compared between treatment arms using a stratified two-sided log-rank test in pairwise comparisons of treatment groups. The analysis population will be the 0702-enrolled population, with data from CIBMTR included.

Event-Free Survival

Event-free survival (EFS) time will be calculated as the time from randomization on the BMT CTN 0702 protocol to death, progression, second primary malignancy, loss to follow-up or the end of the study, whichever comes first. Patients alive at the time of last observation or lost to follow-up will be censored at the date of last contact. The analysis population will be the 0702-enrolled population with follow up data from the CIBMTR included as needed. The Kaplan-Meier estimate of EFS will be estimated at 5 years post randomization on the BMT CTN 0702 protocol along with corresponding 98.3% confidence intervals. Event-free survival will be compared between treatment arms using a stratified, two-sided log-rank test in pairwise comparisons of treatment groups.

Second Primary Malignancies

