4.3 Supplemental Analyses

A supplemental analysis of OS will be included in which OS is analyzed using Cox regression, with treatment arm and risk strata as covariates, and will include demographic and baseline characteristics which are statistically different between treatment arms (p<0.1) for covariates specified in section 3.1. Start time will be randomization on BMT CTN 0702 and all participants randomized on 0702 will be included.

Supplemental analysis of EFS will be included.

- The first will analyze EFS using Cox regression, with treatment arm and risk strata as covariates, and will include demographic and baseline characteristics which are statistically different between treatment arms (p<0.1) for covariates specified in section 3.1. Start time will be randomization on BMT CTN 0702 and all participants randomized on 0702 will be included.
- The second will explore cause-specific hazards for each component of EFS. Cox models
 with treatment arm, risk strata, and demographic/baseline covariates as specified above
 will be used. Start time will be randomization on BMT CTN 0702 and all participants
 randomized on 0702 will be included. For each component, the other components of EFS
 will be considered censoring events.
- The third will analyze EFS using Cox regression in the subset of 0702 participants who initiated lenalidomide maintenance therapy. In this model, the outcome will be the time to

progression or death and the start time will be initiation of maintenance lenalidomide. Discontinuation of lenalidomide maintenance will be considered as a time-varying covariate. Treatment group, strata, and baseline covariates used in the first EFS regression analysis will also be included. The limited interpretation will be noted for this analysis, since it will include non-randomized comparisons and there may be bias in who enrolled in BMT CTN 07LT and continued on lenalidomide maintenance.

Supplemental landmark analyses will be included. The endpoints of PFS, OS, and EFS will be explored in the 0702-enrolled population who is alive four years post randomization (OS) or who is alive and progression- or event-free (for PFS and EFS respectively). A log rank test will compare each outcome for the groups determined by those who were taking lenalidomide at four years post randomization compared to those who were not. Kaplan meier estimates of each outcome at 5 years post randomization will be provided for each lenalidomide status group.

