ERC-Adjudicated Deaths								

		Tre	eatmen	t Arm			Т	otal
	Auto/	Auto	Auto	o/RVD	Auto	o/Maint		
	N	%	N	%	N	%	N	%
Primary Cause of Death								
Disease Recurrence or Persistence								
Secondary Malignancy								
[Reason 3]								
[Reason 4]								
Deaths with Cause Not Adjudicated								
Primary Cause of Death								
Disease Recurrence or Persistence								
Secondary Malignancy								
Disease recurrence or persistence/secondary malignancy								
[Reason 4]								
[Reason 5]								

Supplemental Exhibit 07LT-5A: Multivariate Cox Regression Analysis of Overall Survival – 0702 baseline factors

Maximum Likelihood Estimates and Hazard Ratios

		Hazard Rati	0	
Covariate	Point	Confidence	Confidence	Model
	Estimate	limit	limit	Parameter
				Estimate
				p-value
Auto/Auto treatment arm vs				
Auto/Maintenance arm ¹				
Auto/Auto treatment arm vs				
Auto/RVD arm ¹				
Auto/RVD treatment arm vs				
Auto/Maintenance arm ¹				
Risk strata—High risk vs				
Risk strata—Standard risk				
(other adjustment factor as				
needed)				
(other adjustment factor as				
needed)				
(other adjustment factor as				
needed)				

¹P-values are compared to the 0.05/3 significance level.

Figure: A forest plot for the hazard ratios and confidence intervals may also be provided.

Notes for this secondary analysis:

Model covariates:

- Treatment group
- Randomized risk strata
- Any of the factors in column 2 of the table in Section 3.1 that have a test for treatment group differences that is significant at the 0.1 level. ERC-adjudicated baseline disease response will be tested using 2 categorizations (CR or better, VGPR or better). If both are significant at the 0.1 level, the one that is more significant will be used in the model.
- No interactions will be included.

- Analysis population is 0702 participants
- Time to OS is calculated from randomization
- proc phreg in SAS, no model selection procedures

Supplemental Exhibit 07LT-5B: Multivariate Cox Regression Analysis of Overall Survival from Initiation of Lenalidomide

Maximum Likelihood Estimates and Hazard Ratios

		0		
Covariate	Point Estimate	Lower Confidence Limit	Upper Confidence Limit	Model Parameter Estimate p-value
Auto/Auto treatment arm vs Auto/Maintenance arm ¹				
Auto/Auto treatment arm vs Auto/RVD arm ¹				
Auto/RVD treatment arm vs Auto/Maintenance arm ¹				
Risk strata—High risk vs Risk strata—Standard risk				
Permanent discontinuation of lenalidomide (time-dependent)				

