(other adjustment factor as needed)				
(other adjustment factor as needed)				
(other adjustment factor as needed)				

¹ P-values are compared to the 0.05/3 significance level.

Figure: A forest plot for the hazard ratios and confidence intervals may also be provided.

Notes for this secondary analysis:

Model covariates:

- Treatment group
- Randomized risk strata
- Any of the factors in column 2 of the table in Section 3.1 that have a test for treatment group differences that is significant at the 0.1 level. ERC-adjudicated baseline disease response will be tested using 2 categorizations (CR or better, VGPR or better). If both are significant at the 0.1 level, the one that is more significant will be used in the model.
- No interactions
- Permanent discontinuation of lenalidomide as a time varying covariate.

- Analysis population is 0702 participants who initiated lenalidomide
- Time to PFS is calculated from start time of lenalidomide
- Proc phreg in SAS, no model selection procedure

Supplemental Exhibit 07LT-6A: Multivariate Cox Regression Analysis of Event-free Survival – 0702 baseline factors

Maximum Likelihood Estimates and Hazard Ratios

	Cox model	Parameter		Hazard Rati	0
Covariate	Estimate	p-value	Point	Confidence	Confidence
			Estimate	limit	limit
Auto/Auto treatment arm vs					
Auto/Maintenance arm ¹					
Auto/Auto treatment arm vs Auto/RVD					
arm ¹					
Auto/RVD treatment arm vs					
Auto/Maintenance arm ¹					
Risk strata—High risk vs					
Risk strata—Standard risk					
(other adjustment factor as needed)					
(other adjustment factor as needed)					
(other adjustment factor as needed)					

¹P-values are compared to the 0.05/3 significance level.

Figure: A forest plot for the hazard ratios and confidence intervals may also be provided.

Notes for this secondary analysis:

Model covariates:

- Treatment group
- Randomized risk strata
- Any of the factors in column 2 of the table in Section 3.1 that have a test for treatment group differences that is significant at the 0.1 level. ERC-adjudicated baseline disease response will be tested using 2 categorizations (CR or better, VGPR or better). If both are significant at the 0.1 level, the one that is more significant will be used in the model.
- No interactions will be included.

- Analysis population is 0702 participants
- Time to EFS is calculated from randomization
- proc phreg in SAS, no model selection procedures

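### In Supplemental Exhibit 07LT-5B the hazard ratio for stopping lenalidomide would mainly reflect progression, and the SAP text does not plan this overall survival model

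*SAP*

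**What the plan says.** Supplemental Exhibit 07LT-5B is titled "Multivariate Cox Regression Analysis of Overall Survival from Initiation of Lenalidomide". Its notes give the population as "Analysis population is 0702 participants who initiated lenalidomide". The covariates are treatment group, randomized risk strata, baseline factors that differ between arms at the 0.1 level, and "Permanent discontinuation of lenalidomide as a time varying covariate". Progression is not in the list, and reasons for stopping are not separated. The time note reads "Time to PFS is calculated from start time of lenalidomide", although the title and the contents list both name overall survival.

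Protocol 2.4.1 states: "Patients will continue lenalidomide until disease progression, or discontinuation due to toxicity, death, or withdrawal from the study". SAP 1.4 repeats this. Protocol 2.3.3 bars from 07LT lenalidomide "Patients who have evidence of disease progression prior to enrollment". For overall survival, SAP 4.2 says "The event is death from any cause" and supplements trial data with CIBMTR data; Protocol 4.4.3 sends patients who progress to CIBMTR follow-up.

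The analysis text plans something different for OS. SAP 4.3 says "A supplemental analysis of OS will be included in which OS is analyzed using Cox regression, with treatment arm and risk strata as covariates", starting at randomization and including all randomized patients. SAP 2.8.1 lists a discontinuation model for EFS but none for OS. SAP 4.1 and 4.3 attach a caution about non-randomized comparison to the PFS and EFS discontinuation models. Nothing comparable is attached to 5B.

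**The concern.** Progression is both a main reason for stopping the drug and a strong predictor of death. In 5B the covariate switches to discontinued at progression for patients still on drug, and their later deaths are then counted against stopping. The sibling PFS and EFS models (Exhibits 4B and 6C) do not have this problem, because progression is itself their event and no follow-up remains after it.

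Long-term lenalidomide is a central subject of this study. A table, possibly with a forest plot, showing several-fold higher mortality after permanent discontinuation could be read as a survival benefit of staying on the drug, when the same figure would appear with no such benefit.

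**Working it through.** **No figure to reproduce.** The documents give no event count, power or hazard ratio for 5B. The question is what the model returns when stopping truly has no effect on death.

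**Inputs from the protocol (section 1.2).** Median time to progression on lenalidomide is 46 months. Median survival after first progression is 29 months (lenalidomide group of one cited trial) or, as a milder case, 48 months (its placebo group).

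**Assumed inputs.** Death hazard before progression 0.001 to 0.003 per month; stopping for other reasons 0.005 to 0.030 per month, plus 20% or 40% stopping at 36 months; follow-up 48 to 90 months; time to progression counted from lenalidomide start; drug stopped at progression throughout, including on the parent trial, whose protocol is not among the documents.

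**Hand calculation.** Let h0 be the death hazard before progression, h1 = ln 2 / (median survival after progression), and f the share of post-discontinuation time that falls after progression (taken from the simulation). With no effect of stopping, the crude rate ratio is

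R = [f × h1 + (1 − f) × h0] / h0.

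For row B: h1 = 0.693/29 = 0.0239, f = 0.68, h0 = 0.002, so R = (0.68 × 0.0239 + 0.32 × 0.002)/0.002 = 0.0169/0.002 = 8.4.

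**Simulation.** Start-stop Cox models, mean of six runs of 6,000 patients per row, true effect of stopping HR 1.0.

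| Row | Median after progression (mo) | h0 | Other stops per month (+ at 36 mo) | f | R by hand | 5B HR | HR with progression added | Stops due to progression | Post-stop deaths that follow progression |
|---|---|---|---|---|---|---|---|---|---|
| A | 29 | 0.001 | 0.005 (+20%) | 0.68 | 16.6 | 18.09 | 1.03 | 66% | 98% |
| B | 29 | 0.002 | 0.005 (+20%) | 0.68 | 8.4 | 9.05 | 1.07 | 66% | 96% |
| C | 29 | 0.002 | 0.015 (+40%) | 0.50 | 6.5 | 6.80 | 1.04 | 43% | 92% |
| D | 48 | 0.003 | 0.015 (+40%) | 0.55 | 3.1 | 3.15 | 1.03 | 43% | 86% |
| E | 48 | 0.003 | 0.030 (+40%) | 0.47 | 2.8 | 2.66 | 1.04 | 31% | 81% |

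The hand ratios track the fitted ones. Even in row E, where most stops have other causes, four in five deaths after stopping follow progression.

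A second set of runs used annual rates, all assumed: progression 0.10–0.15, death 0.015 before and 0.08–0.25 after progression, other stops 0.08–0.15, over 4–7.5 years. The 5B hazard ratio was 3.0 to 11.3. In its middle case it was 6.0, falling to 0.99 with only pre-progression stops counted and progression added.

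**When stopping does act directly on death (row C).** True hazard ratios of 0.7, 1.0 and 1.5 gave 5B values of 4.92, 6.80 and 9.71, so a protective effect would still be reported as strong harm. With progression in the model the values were 0.71, 1.04 and 1.52.

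**Would it look significant?** Using z ≈ ln(HR) × √[d × p(1 − p)], with an assumed d = 100 deaths, p = 0.2 to 0.5 of the risk set discontinued, and HR 2.7: z = 0.993 × √16 = 4.0 to 0.993 × √25 = 5.0. Yes, even at the low end.

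**Limit of the two-covariate model.** In the middle case of the second set, stopping was made to multiply the progression hazard by 1.5, 2 or 3. Stopping then truly increases deaths, yet the model with progression included returned 0.99, 1.01 and 1.00. It removes any effect that works through earlier progression.

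**The case against.** The strongest reply is that 5B is only a shell. SAP section 5 calls the templates illustrative, the analysis text does not plan the model, and the PFS note leaves its outcome unsettled; run on PFS time, the problem would not arise. This stands in part: the firmest documentary defect is that the shell and the text disagree. But the section 5 disclaimer concerns layout and wording, and the title and contents list both say OS, so the exhibit may well be produced as labelled.

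A reader might infer that the hazard ratio measures progression and nothing about stopping. The documents do not support that. Toxicity and withdrawal also end treatment, so the estimate is a mixture in which progression dominates.

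A reader might also infer that practically every progressor switches to discontinued on the progression date. Some will have stopped earlier. With stop hazard s, progression hazard p and follow-up T, and ignoring earlier deaths, that share among progressors is 1 − [p/(p + s)] × (1 − e^−(p+s)T)/(1 − e^−pT). It is 13% at p = 0.15, s = 0.08, T = 4 and 36% at p = 0.10, s = 0.15, T = 7.5. The commercial-lenalidomide rule in SAP 4.1, if carried over to 5B, could also leave some patients counted as on drug after progression. These points weaken the link without removing it.

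Finally, adding progression conditions on a main route by which maintenance could affect survival. This objection stands in full and governs how any retained version must be labelled.

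**Conclusion.** The concern holds. As laid out, 5B would report a discontinuation hazard ratio that mainly reflects progression: several-fold above 1, about 3 to 18 under the rates tried, with no true effect of stopping. The direction held in every scenario. The size rests on assumed rates and should not be read as a forecast of the trial's result. The omission from SAP 2.8.1 and 4.3, the missing caution, and the conflict between the OS title and the PFS note are textual facts that need no assumption.

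The consequence is confined to a supplemental, non-randomized table. The primary log-rank test of PFS, the pairwise OS comparisons and the OS Cox model in SAP 4.3 are unaffected. The exhibit should be changed before analysis, but the trial's main conclusions do not depend on it.

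**What to change.** Preferred: delete Supplemental Exhibit 07LT-5B and its entry in the contents list. The SAP analysis text loses nothing.

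If it is kept:

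- Correct the time note to time to death from the start of lenalidomide.
- Describe the model in SAP 4.3 and list it in 2.8.1, with a caveat that the comparison is non-randomized and that progression is a main reason for stopping.
- Switch the discontinuation covariate on only for stops that precede progression or non-protocol therapy, and add progression as a second time-dependent covariate. State whether the commercial-lenalidomide rule of SAP 4.1 applies.
- Label the result as the association of stopping with death that does not act through progression. It excludes any survival effect of stopping through earlier progression, so a value near 1 must not be read as showing that stopping is harmless.

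The cost is SAP wording and one more time-dependent covariate. Progression dates are already needed for the primary endpoint, and discontinuation dates for Exhibit 07LT-4B.

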2.8.1 Changes to the planned analyses

Clarifications from the BMT CTN 07LT protocol

The protocol specified that for the primary endpoint of PFS, deaths will be counted as failures no matter when they occur. This is clarified to note that deaths that occur prior to the end of 2018 will be counted as failures and deaths that occur after progression will use time to progression rather than time to death for the primary analysis. Deaths through the end of follow-up in December 2018 will be counted, but deaths that occur between the end of BMT CTN 07LT in December 2018 and the database closure for the analysis will not be counted.

The protocol specified that for some of the secondary outcomes, the analysis would be completed once all alive patients have been followed for 5-years post randomization on the BMT CTN 0702 protocol. This is clarified to note that the secondary outcomes will be analyzed at the same time as the primary analysis -- once all alive patients have been followed for 5-years post randomization on the BMT CTN 0702 protocol or the end of 2018.

The protocol specified that a Cox model would be used to analyze PFS data, but did not require that treatment group and risk strata be included in the model. These factors will be included in the models.

Supplemental analyses of EFS and OS have been added to incorporate a Cox model analysis adjusting for baseline risk factors for the 0702-enrolled population and to incorporate a Cox model investigating EFS, baseline risk factors, and discontinuation of lenalidomide among the population that initiated maintenance therapy. Additional cause-specific analyses will show the Cox model results for each component of EFS, with censoring at the time of the other components.

Additional supplemental landmark analyses of PFS, OS, and EFS have been added to explore these outcomes between those on long term lenalidomide and those not on long term lenalidomide.

3. Participant Characteristics and Compliance

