Exhibit 07LT-4B: Multivariate Cox Regression Analysis of Progression-free Survival from Initiation of Lenalidomide (Secondary Analysis of PFS)

Maximum Likelihood Estimates and Hazard Ratios

		0		
Covariate	Point Estimate	Lower Confidence Limit	Upper Confidence Limit	Model Parameter Estimate p-value
Auto/Auto treatment arm vs Auto/Maintenance arm¹				
Auto/Auto treatment arm vs Auto/RVD arm ¹				
Auto/RVD treatment arm vs Auto/Maintenance arm ¹				
Risk strata—High risk vs Risk strata—Standard risk				
Permanent discontinuation of lenalidomide (time-dependent)				
(other adjustment factor as needed)				
(other adjustment factor as needed)				
(other adjustment factor as needed)				

¹ P-values are compared to the 0.05/3 significance level.

Figure: A forest plot for the hazard ratios and confidence intervals may also be provided.

Notes for this secondary analysis:

Model covariates:

[figure not shown]
- Treatment group
- Randomized risk strata
- Any of the factors in column 2 of the table in Section 3.1 that have a test for treatment group differences that is significant at the 0.1 level. ERC-adjudicated baseline disease response will be tested using 2 categorizations (CR or better, VGPR or better). If both are significant at the 0.1 level, the one that is more significant will be used in the model.
- No interactions
- Permanent discontinuation of lenalidomide as a time varying covariate.

- Analysis population is 0702 participants who initiated lenalidomide
- Time to PFS is calculated from start time of lenalidomide
- Proc phreg in SAS, no model selection procedure

Exhibit 07LT-5: Overall Survival

Figure template for illustration only

Overall Survival by Treatment Arm

Kaplan Meier Estimates and 98.3% Confidence Intervals

	Auto/Auto	Auto/RVD	Auto/Maint		
5-year Estimates:	XX.X (XX.X, XX.X)	XX.X (XX.X, XX.X)	XX.X (XX.X, XX.X)		

Stratified Log-Rank Test for Treatment Group Differences

[figure not shown]
Treatment Group Comparison	p-value ¹
Auto/Auto vs Auto/RVD	0.XX
Auto/Auto vs Auto/Maint	0.XX
Auto/RVD vs Auto/Maint	0.XX

¹Significance level is 0.05/3 for each pairwise comparison.

Exhibit 07LT-6: Event-Free Survival

Figure template for illustration only

Event-Free Survival by Treatment Arm

Kaplan Meier Estimates and 98.3% Confidence Intervals

	Auto/Auto	Auto/RVD	Auto/Maint		
5-year Estimates:	XX.X (XX.X, XX.X)	XX.X (XX.X, XX.X)	XX.X (XX.X, XX.X)		

Stratified Log-Rank Test for Treatment Group Differences

[figure not shown]

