Supplemental Exhibit 07LT-6B: Cause-specific Multivariate Cox Regression Analysis of the Components of Event-free Survival

Maximum Likelihood Estimates and Hazard Ratios: Event=Progression, Censoring Events=SPM, Death

	Cox model	Parameter		Hazard Rati	0
Covariate	Estimate	p-value	Point		
			Estimate	Confidence limit	Confidence limit
Auto/Auto treatment arm vs					
Auto/Maintenance arm ¹					
Auto/Auto treatment arm vs Auto/RVD					
arm ¹					
Auto/RVD treatment arm vs					
Auto/Maintenance arm ¹					
Risk strata—High risk vs					
Risk strata—Standard risk					
Permanent discontinuation of					
lenalidomide					
(other adjustment factor as needed)					
(other adjustment factor as needed)					
(other adjustment factor as needed)					

¹ P-values are compared to the 0.05/3 significance level.

Maximum Likelihood Estimates and Hazard Ratios: Event=SPM, Censoring Events=Progression, Death

	Cox model	Parameter		Hazard Rati	0
Covariate	Estimate	p-value	Point Estimate	Confidence limit	Confidence limit
Auto/Auto treatment arm vs Auto/Maintenance arm ¹					
Auto/Auto treatment arm vs Auto/RVD arm ¹					
Auto/RVD treatment arm vs Auto/Maintenance arm ¹					
Risk strata—High risk vs Risk strata—Standard risk					
Permanent discontinuation of lenalidomide					
(other adjustment factor as needed)					
(other adjustment factor as needed)	· ·				
(other adjustment factor as needed)					

¹ P-values are compared to the 0.05/3 significance level.

Maximum Likelihood Estimates and Hazard Ratios: Event=Death, Censoring Events=Progression, SPM

	Cox model	Parameter		Hazard Rati	0
Covariate	Estimate	p-value	Point		
			Estimate	Confidence limit	Confidence limit
Auto/Auto treatment arm vs Auto/Maintenance arm ¹					
Auto/Auto treatment arm vs Auto/RVD					
arm ¹					
Auto/RVD treatment arm vs					
Auto/Maintenance arm ¹					
Risk strata—High risk vs					
Risk strata—Standard risk					
Permanent discontinuation of					
lenalidomide					
(other adjustment factor as needed)					
(other adjustment factor as needed)					
(other adjustment factor as needed)					

¹ P-values are compared to the 0.05/3 significance level.

Figure: A forest plot for the hazard ratios and confidence intervals may also be provided.

Supplemental Exhibit 07LT-6C: Multivariate Cox Regression Analysis of Event-free Survival from Initiation of Lenalidomide

Maximum Likelihood Estimates and Hazard Ratios

[figure not shown]
	Cox model	Parameter		Hazard Rati	0
Covariate	Estimate	p-value	Point		

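### Supplemental Exhibit 07LT-6B adds lenalidomide discontinuation to the cause-specific EFS models, which SAP 4.3 limits to arm, risk strata and baseline covariates

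*SAP*

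**What the plan says.** SAP 4.3 (Supplemental Analyses) lists three EFS regressions.

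- The first is an all-cause EFS Cox model from randomization (shell: Exhibit 6A).
- The second gives cause-specific hazards for the EFS components (shell: Exhibit 6B). Its Cox models are to be fitted "with treatment arm, risk strata, and demographic/baseline covariates as specified above". On timing and population it says "Start time will be randomization on BMT CTN 0702 and all participants" randomized on 0702 are included.
- The third (shell: Exhibit 6C) is where lenalidomide enters: "The third will analyze EFS using Cox regression in the subset of 0702 participants who initiated lenalidomide maintenance therapy". Time runs from the start of maintenance, and "Discontinuation of lenalidomide maintenance will be considered as a time-varying covariate". The SAP adds that interpretation is limited because the comparisons are not randomized.

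SAP 2.8.1 draws the same line. Its entry for the second analysis reads "Additional cause-specific analyses will show the Cox model results for each component of EFS, with censoring at the time of the other components" and does not mention discontinuation.

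The shells in the appendix differ from this. Each of the three Exhibit 6B tables has the row "Permanent discontinuation of lenalidomide", listed with the arm contrasts, which are tested at 0.05/3. Exhibit 6B has no notes on population, start time or covariates. In the initiator-only shells 4B and 5B the row reads "Permanent discontinuation of lenalidomide (time-dependent", with the label's parenthesis closing there, and a note states "Analysis population is 0702 participants who initiated lenalidomide".

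**The concern.** A programmer working from SAP 4.3 and one working from the Exhibit 6B shell would fit different models and report different hazard ratios under the same exhibit number.

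The difference is one of substance. The arms diverge before maintenance begins: a second transplant, RVD consolidation, or neither (SAP 1.1). Starting lenalidomide and staying on it both come after randomization and could differ by arm; Exhibit 07LT-1 itself plans to report starts by arm. An arm hazard ratio adjusted for discontinuation is no longer the comparison that 4.3 describes. Part of an arm effect that runs through maintenance could be adjusted away.

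The discontinuation hazard ratio has its own problem. In a population of all randomized patients, some never start the drug and so cannot stop it. Neither document says how they are to be coded. The caution that 4.1 and 4.3 attach to their discontinuation models does not appear on Exhibit 6B.

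**Working it through.** **1. Figures in the documents.** The arm sizes in the shells add up: 247 + 254 + 257 = 758, the number in SAP 2.1. The pairwise level is 0.05/3 = 0.01667, and 1 − 0.01667 = 98.3%, the confidence level in SAP 2.3. Neither figure changes if the row is deleted.

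**2. Text against shells, EFS models only.**

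| Item | SAP 4.3 | Appendix shell |
|---|---|---|
| First model (6A) | arm, strata, baseline; from randomization; all randomized | agrees; no discontinuation row; notes present |
| Second model (6B) | arm, strata, baseline; from randomization; all randomized | discontinuation row in all three tables; no notes |
| Third model (6C) | initiators; from start of maintenance; discontinuation time-varying | discontinuation row, not labelled time-dependent; no notes |

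The conflict is confined to one row of 6B. Population and start time for the second model come from 4.3 and are not contradicted.

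**3. Could it matter numerically?** The documents give no rates of starting or stopping by arm, so any size rests on assumptions. A simulation used:

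- two arms (A/B) of 254 and 60 months of follow-up;
- a single combined event with hazard 0.010 per month on drug, and no direct arm effect;
- maintenance starting at 4–6 months in arm A and 6–8 months in arm B;
- a shared frailty (SD 0.7 on the log scale) that raises the event hazard, the chance of never starting and the rate of stopping;
- 25 replicates per scenario.

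Discontinuation was entered as time-varying. Never-starters were coded either 0 (not discontinued) or 1 (off drug throughout).

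| Never start A/B | Stop per month A/B | True off/on HR | Arm HR, no covariate | Arm HR, coded 0 | Arm HR, coded 1 | Discontinuation HR, coded 0 | Discontinuation HR, coded 1 |
|---|---|---|---|---|---|---|---|
| 10/10% | 0.015/0.015 | 1.6 | 1.00 | 1.00 | 1.01 | 1.67 | 2.02 |
| 10/10% | 0.01/0.03 | 1.6 | 1.08 | 0.99 | 0.96 | 1.63 | 2.01 |
| 5/25% | 0.015/0.015 | 1.6 | 1.05 | 1.08 | 0.96 | 1.57 | 2.10 |
| 5/25% | 0.01/0.03 | 1.6 | 1.13 | 1.08 | 0.91 | 1.44 | 2.06 |
| 10/10% | 0.01/0.03 | 2.0 | 1.11 | 0.97 | 0.94 | 1.95 | 2.43 |
| 10/30% | 0.015/0.015 | 2.0 | 1.04 | 1.07 | 0.93 | 1.77 | 2.58 |

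**4. Reading the table.** With equal rates the arm hazard ratio barely moves (1.00, 1.00, 1.01). With unequal rates, coding 0 shifts it by between 0.03 (1.05 to 1.08) and 0.14 (1.11 to 0.97). Coding 1 shifts it by up to 0.22 (1.13 to 0.91). The discontinuation hazard ratio depends on the coding in every row: 1.44–1.95 under coding 0 against 2.01–2.58 under coding 1, for true values of 1.6 or 2.0.

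**5. Precision.** Events occurred in 46–50% of 508 patients, about 234 to 254. The standard error of a log arm HR is roughly 2/√234 = 0.13 per replicate, or 0.13/√25 = 0.026 for a mean of 25. Shifts compare models fitted to the same data, so they are firmer than the separate values, but the smallest should not be over-read.

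**The case against.** The strongest reply is that the body text already specifies the right model. SAP 5 describes the shells as illustrative, the analysis is supplemental and exploratory, and the row may simply have been carried over from an initiator-only shell. Much of this stands, and it is why the point is minor. It does not remove the conflict: the illustration clause covers layout, wording and editorial change, whereas a model covariate is analysis content. The row also appears in all three tables, with no note to correct it.

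Several stronger readings are tempting, but the documents do not support them.

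- *The row is a fixed covariate, so future stopping defines a baseline group.* A reader might infer this because 4B and 5B say time-dependent and 6B does not. But 6C also lacks the label, and 4.3 makes that model time-varying. A missing label in these shells does not show a fixed term.
- *Never-starters count as not discontinued.* This is the natural default of a 0/1 variable, but no coding rule is written. They could be coded off drug, or be dropped as missing, which would contradict the inclusion of everyone randomized.
- *6B is the only output that separates the components by arm.* Exhibit 07LT-6 counts first events by type and arm, and Exhibit 07LT-7 gives SPM incidence by arm with Gray's tests. 6B is only the component-wise regression.
- *The arm effect is necessarily distorted.* In the simulation this required starting or stopping rates that differ by arm, and the documents report no such rates.

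**Conclusion.** The concern holds as an inconsistency between text and shell: Exhibit 6B carries a post-randomization treatment covariate that SAP 4.3 does not allow in these models. This rests on the wording alone and needs no simulation.

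The consequence is conditional. If the shell were fitted, the arm hazard ratios would not be the comparison described in 4.3, and they could be distorted if starting or stopping lenalidomide differs by arm. The discontinuation hazard ratio would depend on an unstated coding choice. The simulated shifts show plausible sizes under assumed rates; they are not estimates for this trial, and they model one combined event rather than the three components.

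Severity is minor. The primary PFS log-rank test and the secondary OS, EFS and SPM tests do not use this model.

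**What to change.** Delete the discontinuation row from all three Exhibit 6B tables so that they match SAP 4.3. Add the notes that Exhibit 6A carries: covariates, analysis population (all 0702 participants) and start time (randomization).

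If component results by lenalidomide exposure are wanted, specify them in 4.3 and give them a separate table among patients who started maintenance. Time should run from that start, with discontinuation explicitly time-varying and the same limited-interpretation caveat as the third EFS model.

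The cost is an edit to one set of table shells. No data, patients, sample size or significance level change.
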